Research question

Does a 12-week course of a nutraceutical product containing a combination of vitamin D3, vitamin B3 (niacinamide), vitamin C, omega 3 fatty acids (DHA/EPA), olive polyphenols, resveratrol and astaxanthin improve measures of biological and immune ageing, quality of life, and physical function (Short Physical Performance Battery, SPPB) in healthy older people?

Objectives

To test the hypothesis that a 12-week treatment of Essentials, a nutritional supplement developed by Bayer, will improve biological ageing, immune ageing, quality of life (QoL), and physical function (SPPB) in healthy older adults, by conducting an uncontrolled open label trial in 76 participants.

Essentials composition:

- Vitamin D (20 μg)
- Vitamin C (85 mg)
- Vitamin B3, as niacinamide (50 mg)
- Omega 3 PUFA, EPA + DHA (250 mg)
- Resveratrol (30 mg)
- Olive fruit extract (50 mg), delivering hydroxytyrosol (10 mg)
- Astaxanthin (3.2 mg)

Outcome

An uncontrolled open-label trial, of a 12-week intervention of the Essentials supplement.

85 participants will be recruited to allow for 9 drop outs.

Data will be collected pre-intervention to test:

- Biological ageing by DNA methylation in peripheral blood and saliva;
- Immune ageing by measuring 51 different serum cytokines, chemokines and growth factors to give an iAGE score (Sayed et al 2021), hs-CRP will also be measured;
- QoL (SF36) and diet (7 day food diary, to confirm there was no significant change in the diet of the participants) from questionnaires;
- Physical function assessed by the SPPB (Guralink et al. 1994).

Data collection will be repeated after the 12-week intervention, with the exception of QoL questionnaires which will additionally also be taken at 4 and 8 weeks in to the intervention.

Data analysis will compare differences within groups between pre-intervention and 12 week measures.

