Venous blood will be collected to process serum and will also be collected in to a PAX tube for isolation of DNA. The serum will be used for measurement of the inflammatory immune clock of ageing (iAGE) which is based upon the levels of 51 different cytokines, chemokines and growth factors (Sayed et al. 2021). The measurement will be carried out using a multiplex based methodology. The DNA isolated from the PAX tube will be analysed for DNA methylation using the Illumina EPIC array and the data analysed using both the Horvath (Horvath 2013) and Hannum (Hannum et al. 2013) epigenetic clocks of biological ageing. A second assessment of epigenetic age will be conducted on saliva samples by the company Chronomics. The difference between

chronological age and iAGE will then be calculated as a measure of immune ageing and the epigenetic clock age will establish the degree of overall biological ageing. High sensitivity C-reactive protein from blood will be measured by ELISA.

Study setting

Participants will be invited to attend the Clinical Research Facility at the University Hospital Birmingham where all trial procedures will take place.

Participant recruitment

Eligibility Criteria

The study population is healthy older people.

Inclusion criteria

- Age ≥60 years.
- Ability to provide informed consent.
- Willing to stop taking multivitamins, and dietary supplements containing vitamins C and D, B3, DHA/EPA, Olive polyphenols, resveratrol and astaxanthin or food/beverage products supplemented with the above ingredients 2 weeks prior to and throughout the study.
- Able to travel to the clinic for initial and subsequent evaluations.

Exclusion criteria

- Current smokers, or ex smokers who have stopped within the last 12 months, or are using nicotine replacement products.
- History of diabetes, myocardial infarction, congestive heart failure, kidney failure, liver disease or stroke.
- Untreated thyroid disorder, cancer, active neoplasms.
- Untreated gastrointestinal, or pulmonary diseases.
- Surgery or trauma in last 60 days.
- Inflammatory diseases, auto immune diseases or recent infection in last 60 days.
- Allergies to any of the ingredients to be studied.
- Currently taking or using multivitamins or dietary supplements containing vitamins C and D, B3, DHA/EPA, Olive polyphenols, resveratrol and astaxanthin or food/beverage products supplemented with the above ingredients.
- Currently taking medication known to be metabolised by CYP3A.

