- Currently taking any of the following medications, which confound the effects of inflammation: Tamoxifen, Cyclosporine A, immunosuppressants or Anti TNF inhibitors, NSAIDs.
- Currently taking any of the following anticoagulant drugs (blood thinners): Warfarin, Direct oral anticoagulant drugs (DOACs), and antiplatelet drugs including aspirin.
- Individuals at risk of bleeding complications, including those with inherited bleeding disorders (such as haemophilia), or increased risk hemorrhagic stroke or events.
- Unable or unwilling to maintain current lifestyle throughout study such as eating habits, exercise habits, etc.
- Assessed as being frail by Fried phenotype criteria.

Recruitment target

76 healthy older adults required, so we will aim for 85 recruited to allow for drop outs.

Size of recruitment target

Our sample size calculation is based on iAGE measurements from a previous study of a nutraceutical intervention in adults by Bayer. The number of participants required at 80% power and a significance level of 0.05 to detect a mean difference of 1.5 years in the iAGE score would be 76. To allow for an approximate 10% drop out we will recruit 85 participants.

Recruitment technique

Participants will be invited by contact through the 1000 Elders database. The 1000 Elders is a database of research active healthy older people who have consented to be contacted about studies run through the University of Birmingham. Names, addresses and contact details (telephone and email) are stored complying fully with DPA and CPRD legislation. The invitation will be in the form of an email. This will include an attached PIS, summary of the study, and an invitation to contact the research team if they would be interested in taking part.

Recruitment

Potential participants will contact the study team via email or telephone to express an interest to join the study. At this point eligibility screening will take place, either by telephone or through email communication

Participant identification

Eligible people will then be invited to the Clinical Research Facility at Queen Elizabeth Hospital Birmingham for the initial visit. Reasonable travel expenses will be paid to participants.

Consent

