Computers used to collate the data will have limited access measures via user names and passwords.

Published results will not contain any personal data that could allow identification of individual participants.

GP Notification

We will inform he GP of the participants involvement in the study if the participant consents to this

Safety reporting

An adverse event (AE) is any untoward medical event affecting a clinical trial participant. Each initial AE will be considered for severity, causality or expectedness and may be reclassified as a serious event or reaction based on prevailing circumstances.

An adverse reaction (AR) is where it is suspected that an AE has been caused by a reaction to the trial supplement

A serious adverse event (SAE), serious adverse reaction (SAR) or suspected unexpected serious adverse reaction (SUSAR) is any AE, AR or UAR that at any dose:

- results in death
- is life threatening
- requires hospitalisation or prolongation of existing hospitalisation
- results in persistent or significant disability or incapacity
- is a congenital anomaly or birth defect
- Or is otherwise considered serious

Note: Hospitalisations for treatment planned prior to consent and hospitalisation for elective treatment of a pre-existing condition will not be considered as an SAE. However any adverse events occurring during such hospitalisation will be recorded. Adverse events, adverse reactions and serious adverse events will be reported by participants or other health care professionals.

A telephone contact will be made at 4 and 8 weeks to ensure no adverse events are missed.

All AEs and SAEs will be recorded from the time a participant consents to join the study until the last study visit. Participants with unresolved AEs at the last study visit will be followed up until resolution or 30 days after last visit of that participant, whichever is sooner. SUSARS will be followed until resolution.

The CI, or delegate will ask about the occurrence of AEs and hospitalisations at every telephone check (week 4 and 8) and at the second/final study visit (week 12). AEs will be recorded on the AE Log in the CRF. SAEs will be submitted on an SAE form to the Sponsor within 24 hours of becoming aware of the SAE. SAEs will be assessed for expectedness and causality by the Investigator. The evaluation of expectedness will be made based on the knowledge of the reaction and the relevant product information.

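### The surgery exclusion looks back 60 days from entry but does not name surgery already planned before the Week 12 sample

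*Protocol*

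**What the plan says.** The Protocol's Exclusion criteria bar people with "Surgery or trauma in last 60 days". The same list bars "Inflammatory diseases, auto immune diseases or recent infection in last 60 days". Both windows run backwards from entry.

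The criteria that look forward concern stopping supplements, being able to travel to the clinic, and lifestyle. The last of these excludes anyone "Unable or unwilling to maintain current lifestyle throughout study such as eating habits, exercise habits, etc". None of them names surgery or a planned admission.

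The Safety reporting section says: "Hospitalisations for treatment planned prior to consent and hospitalisation for elective treatment of a pre-existing condition will not be considered as an SAE". It adds: "However any adverse events occurring during such hospitalisation will be recorded". Adverse events are recorded from consent to the last visit, so these sentences can apply to a participant who is on study.

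Under Outcome, baseline includes "Immune ageing by measuring 51 different serum cytokines, chemokines and growth factors to give an iAGE score", with hs-CRP alongside. "Data collection will be repeated after the 12-week intervention", and the visit table puts the second blood sample at Day 84. On the comparison, the plan says: "Data analysis will compare differences within groups between pre-intervention and 12 week measures". There is no control arm.

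**The concern.** iAGE and hs-CRP are inflammatory measures. The protocol gives no reason for its 60-day surgery rule. It stands next to a 60-day rule for infection, and the natural reading is that a recent operation makes the sample unfit for measuring a person's usual inflammatory state.

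The outcome is a difference between two samples, and each enters it with equal weight. The rule protects only the first. A volunteer whose operation is booked for the middle of the study meets every criterion that names surgery, although the problem can be known on the day of consent. This is separate from unforeseen illness or injury after entry, which no entry rule can prevent.

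In a randomised trial such events would tend to fall in both arms. Here they go straight into the estimated 12-week change, and from there into the comparison that the sample size was built on.

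**Working it through.** **1. The exposed part of follow-up.** Inputs: the 60-day window (Exclusion criteria) and the second sample at Day 84 (visit table).

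- Earliest day on which an operation falls within 60 days of the second sample: 84 − 60 = Day 24.
- Share of follow-up: 60/84 = 71%.

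An operation before about Day 24 is outside the protocol's own window and is not part of this point.

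**2. The plan's own figures.** Inputs from Size of recruitment target: 76 participants, 80% power, significance level 0.05, a mean difference of 1.5 years in iAGE, and about 10% drop-out.

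- Recruitment: 76/(1 − 0.10) = 84.4, rounded up to 85. This matches the plan.
- The 76 cannot be rebuilt directly because no SD is given, so I solved for the SD of the within-person change that it implies. Assumption: a two-sided test, as the plan does not state the sidedness.
- Normal formula: SD = 1.5 × √76/(1.960 + 0.842) = 1.5 × 8.718/2.802 = 4.67 years. The paired t-test gives 4.61 years.

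**3. Illustration of size.** The document gives neither the number of people affected, k, nor the rise in iAGE that surgery causes, s. Both are assumed here. With k of 76 affected:

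- shift in mean change = k × s/76
- net effect = 1.5 − k × s/76
- SD* = √(4.67² + (k/76)(1 − k/76)s²)
- power = Φ(net effect × √76/SD* − 1.960)

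Worked case, k = 1 and s = 3: shift 3/76 = 0.04; net 1.461; SD* = 4.68; 1.461 × 8.718/4.68 = 2.72; Φ(2.72 − 1.96) = Φ(0.76) = 78%.

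| People affected (assumed) | Rise in iAGE, years (assumed) | Shift in mean, years | Power |
|---|---|---|---|
| 0 | – | 0 | 80% |
| 1 | 3 | 0.04 | 78% |
| 2 | 5 | 0.13 | 71% |
| 4 | 5 | 0.26 | 61% |
| 4 | 10 | 0.53 | 37% |

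Simulating the paired t-test with SD 4.61 agrees to within about 2 percentage points (78%, 71%, 62% and 36% for the four affected cases). The last two rows show how the result behaves under severe assumptions. They are not forecasts.

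**4. If affected people were set aside instead.** With SD 4.61 and the paired t-test, power is 77.8% at n = 72 (four lost from 76) and 82.5% at n = 81 (four lost from 85 with no other drop-out).

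**The case against.** The strongest reply is that the gap is narrower than it looks. The lifestyle exclusion looks forward, covers inability as well as unwillingness, and is open-ended. An investigator could reasonably apply it to someone awaiting a major operation, and the medical history at Visit 1 gives an occasion to do so. The operations most likely to disturb iAGE are also the ones most likely to be caught this way. This stands in part. The criterion may catch some major operations, but it does not mention surgery, and its examples are eating and exercise, so its use would vary with the person applying it.

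A reader might infer from the safety section that the protocol expects surgical patients in the trial, or that the two sections contradict each other. Neither follows. The safety sentence is a general rule for classifying events and speaks of treatment, not surgery. It allows for such admissions without predicting them. One section sets entry and the other classifies events.

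A reader might also infer a serious loss of power. That rests entirely on assumed counts and assumed rises. The volunteers are healthy and not frail, and they are screened for many conditions and medicines, so few may have surgery booked. The plan recruits 85, which leaves some room, though those nine places are meant for ordinary drop-out. How an affected Week 12 sample is analysed may be settled in a statistical analysis plan that is not shown, and is not counted as missing here. Such a plan would not change who is enrolled.

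**Conclusion.** The point holds as a cheap improvement to the entry criteria. The baseline sample has an explicit 60-day protection from surgery, and the Week 12 sample has none against surgery already known at consent. The exposed period is about Day 24 to Day 84.

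The size cannot be taken from the document. On mild assumptions the shift in mean iAGE change is 0.04 to 0.13 year against a target of 1.5, and power falls from 80% to between 78% and 71%. This rests on a two-sided paired test, an implied SD of change of about 4.6 to 4.7 years, and assumed numbers affected and rises in iAGE.

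It would be tempting to say that the gap could produce a falsely positive trial. The reasoning does not support that for iAGE: a post-operative rise in inflammation works against the supplement, so it would more likely mask a benefit. For SPPB and SF-36 the document gives no basis for a direction, since elective treatment may worsen or improve function by Week 12.

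**What to change.** Extend the existing surgery exclusion so that it also covers surgery known at consent to be planned before the Week 12 visit. Ask about it in the telephone or email screening that the Recruitment section already provides, and confirm it at Visit 1 with the other criteria. A deferred volunteer can enter later, once the existing 60-day rule is met.

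The cost is one line in the criteria and one screening question. The downside is that a few volunteers are deferred. No visit is added, and the targets of 76 and 85 do not change.

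The exemption of planned admissions from serious adverse event status should stay as it is. Narrowing it would change safety reporting and do nothing to protect the Week 12 sample.

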The Sponsor, together with the CI, is responsible for reporting SUSARs to the competent authority, the Research Ethics Committee (REC) and any other competent authorities. Fatal or life threatening SUSARs will be reported within 7 days and non-fatal and non-life threatening SUSARs within 15 days.

Ethical and regulatory considerations

The trial will fit within existing ethical and regulatory frameworks. Participants are healthy volunteers, and not recruited as NHS patients. However, as the recruitment and assessments will take place within an NHS institution we will secure approval through the Health Research Authority (HRA) and an NHS Research Ethics Committee (REC).

The trial product is a nutraceutical, and all components are safe. As such we do not expect the product to present any risks to participants. There are potential benefits to the participants from the product. Application will be made for ethical approval through the HRA, NHS REC, and Hospital trust approval through R+D and Clinical Research Facility governance processes. The study will be sponsored by the University of Birmingham.

Assessment and management of risk

Resveratrol	Minor or none, GI adverse effects in high doses. Safe up to 450mg/day, does in trial is 30mg/day. Resveratrol has been shown to inhibit metabolism of drugs through the CY3PA enzyme. There is a risk of interaction with drugs metabolised by CYP3A if doses >1000mg/day, and long term.
	Studies up to 12 months
Astaxanthin	Minor or none serious adverse effects reported (GI – increased bowel movements, red stool colouration). Safe up to 8mg/day, dose in trial 4mg/day No recognised drug interactions.
	Studies up to 24 months
Vitamin C, D and B3	No concerns about safety at trial doses
Olive derived polyphenols	No concerns about safety
DHA and EPA	Theoretic risk if >6g/day of interaction with warfarin, but no evidence found in reviews. Dose in trial 250mg/day

Full safety details in Appendix 1

To mitigate any potential risks of drug interactions we will exclude people taking anticoagulants, antiplatelets, or drugs metabolised by the CYP3A system

Research Ethics Committee (REC) and other Regulatory review & reports

Before the start of the study, a favourable opinion will be sought from UK NHS Health Research Authority and NHS REC for the study protocol, informed consent forms, patient information sheets, and initial invitation.

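### The SAE exemption for elective admissions for pre-existing conditions has no limit for conditions that worsened after consent, and so conflicts with the protocol's own hospitalisation criterion

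*Protocol*

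**What the plan says.** The Protocol's Safety reporting section lists the outcomes that make an AE serious. One is that the event "requires hospitalisation or prolongation of existing hospitalisation"; the last is the open item "Or is otherwise considered serious".

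A Note directly after the list removes two kinds of admission: "Hospitalisations for treatment planned prior to consent and hospitalisation for elective treatment of a pre-existing condition will not be considered as an SAE". It adds one safeguard: "However any adverse events occurring during such hospitalisation will be recorded".

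Two other statements in the section matter here. Every AE is to be considered on first report for how severe it is, whether it is related and whether it was expected, and it "may be reclassified as a serious event or reaction based on prevailing circumstances". Reporting to the Sponsor depends on SAE status: "SAEs will be submitted on an SAE form to the Sponsor within 24 hours of becoming aware of the SAE". The section ends with SUSAR reporting to the authorities and the ethics committee, within 7 or 15 days depending on the outcome.

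**The concern.** The two halves of the Note differ in kind. Treatment planned before consent cannot have been prompted by the supplement, because capsules are handed out only at the baseline visit, where consent is taken. Elective treatment of a pre-existing condition carries no such guarantee. The condition existed before entry, but the need for admission may have arisen afterwards, while the participant was taking the capsules.

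An exemption for elective admissions usually serves to keep admissions that say nothing about the product out of the SAE listing. As worded, this one also keeps out admissions that might say something. The trial has no control arm, so there is no comparison group in which an excess of such admissions could show up. The review of individual cases therefore carries most of the safety evaluation. What is at stake is whether a suspected reaction that leads to an elective admission must be escalated, or only may be.

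**Working it through.** The point turns on wording, so the check sets the statements side by side. The protocol has no figure to reproduce. All statements are from Safety reporting unless noted.

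1. **What the second half adds.** Elective admissions for a pre-existing condition were either planned before consent or arranged after it. The first half already exempts those planned before. The second half has effect of its own only on those arranged after consent.

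2. **Whether it is limited elsewhere.** Neither the Note nor any other section restricts it to stable conditions or to admissions unrelated to the supplement.

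3. **Whether such a participant can enter.** Exclusion criteria lists "Untreated gastrointestinal, or pulmonary diseases", so treated disease of these kinds is not excluded by that item. Other items remove much else: a history of diabetes, myocardial infarction, heart failure, kidney failure, liver disease or stroke; inflammatory and autoimmune disease; bleeding risk; frailty; and users of several drug classes. The remaining pool is restricted but not empty.

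4. **Tracing a case.** A pre-existing, treated condition worsens after the capsules are started, and an elective admission is arranged.
   - The worsening is an untoward medical event, so it is an AE. If the supplement is suspected, it is an adverse reaction.
   - Under the seriousness list, it led to hospitalisation and is serious.
   - Under the Note, the admission is for elective treatment of a pre-existing condition and is not an SAE.
   - If no other seriousness criterion is met, the two rules give opposite answers.

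5. **Whether the attached safeguard helps.** The follow-on sentence covers events during the stay. The worsening came before the stay and is not reached. The sentence also requires recording, not SAE assessment.

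6. **What follows if the Note is applied literally.** No SAE form and no 24-hour report are required. A SUSAR must first be serious, so its 7- or 15-day clock does not start. The event stays on the AE log unless the investigator escalates it.

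7. **Scale.** With all 85 recruits followed for 12 weeks, exposure is 85 × 12/52 = 19.6 person-years. With only the 76 allowed-for completers counted, it is 76 × 12/52 = 17.5. One misclassified admission is 1/85 = 1.2% of participants. The documents give no rate of elective admission, so no expected number of affected cases can be derived.

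**The case against.** Four arguments on the other side have force.

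**The Note may exempt only the admission.** An investigator could treat the worsening as its own AE, test it against the hospitalisation criterion and report it. An investigator could also hold that an admission forced by new deterioration is more than elective treatment of a pre-existing condition. Both readings are reasonable, but the text requires neither. Two investigators could class the same case differently, which is itself a reason to reconcile the wording.

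**Other routes exist.** Causality is considered for every AE, not only for SAEs. The open seriousness item and the reclassification sentence both allow escalation. Staff ask about AEs and hospitalisations at weeks 4, 8 and 12, so the admission should come to light. Unresolved AEs are followed for up to 30 days after the last visit. All of this stands, and it means that the event is not lost from the record. But the two escalation routes are discretionary, while the Note is categorical.

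**The product looks low-risk.** Under Assessment and management of risk, the resveratrol entry reads "Minor or none, GI adverse effects in high doses", and the stated trial dose is 30/450, or one fifteenth, of the amount that the table calls safe. The astaxanthin effects listed are minor bowel changes. A reader might infer that the exemption removes just the admissions in which a reaction to this product would appear. The documents do not support that: nothing in the table points to reactions leading to elective admission.

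**The population is selected.** A reader might infer from the wording on untreated disease that most chronic illness is admitted. The full list of exclusions shows otherwise.

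**Conclusion.** The point holds as a wording conflict of minor severity. Read literally, the Note lets a worsening that led to an elective admission fall outside mandatory SAE reporting, although the list just above it calls the same event serious. The gap is confined to elective admissions, arranged after consent, for a pre-existing condition that worsened, where no other seriousness criterion is met. Deaths, life-threatening and disabling events and emergency admissions remain SAEs.

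A reader might go further and infer that SAE and SUSAR reporting can never be triggered in such a case, or that the trial's SAE count is biased by some stated amount. The first does not follow, because the investigator may escalate. The second cannot be shown, because any number of missed events would rest on an admission rate that the documents do not give, and on every such case going unescalated. In a short study of healthy volunteers the number is likely to be small. The outcomes named in the Protocol are ageing clocks, hs-CRP, quality of life and physical function, and none of their analyses uses the SAE count.

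The conclusion assumes only that site staff apply the Note as written.

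**What to change.** Reconcile the Note with the seriousness criteria by limiting its second half: an elective admission for a pre-existing condition is exempt only if the condition has not worsened since consent. State that a worsening that leads to hospitalisation is recorded as an AE, with onset at the time of worsening, and assessed as an SAE. The first half can stay as it is, and admissions for stable conditions arranged after consent remain exempt.

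The cost is one clause in a protocol amendment and at most a few extra SAE forms. No assessment, visit, sample size or analysis changes.
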